STATISTICAL CONSIDERATIONS	
Sample size determination: No formal sample size calculations have been performed. Sample size for this study was based upon empirical considerations.
 
Analysis population: The primary analysis population for Stage 1 and the overall study is the safety population, which is defined as all patients who received at least 1 infusion (partial or total) in the study. The primary analysis population for Stage 2 (Cohort 3) is the modified intent-to-treat (mITT) population, defined as all randomized patients in Cohort 3 who received at least 1 infusion and with evaluable baseline efficacy assessment.
 
Analysis of safety: Safety analyses will be performed using the safety population. All AEs will be coded using the most recent version of the Medical Dictionary for Regulatory Activities (MedDRA). Adverse event incidence tables will be presented by system organ class (SOC) sorted by internationally agreed order, preferred term (PT), and the number and percentage of patients experiencing an AE. Multiple occurrences of the same event in the same patient will be counted only once in the tables within a considered period. The denominator for computation of percentages is the safety population. All TEAEs, all TEAEs potentially related to study drug, all TEAEs leading to treatment discontinuation, all TEAEs that are IARs, all treatment-emergent serious adverse events (SAEs), including treatment-related SAEs, and all AEs with fatal outcome will be summarized descriptively. Additional safety data including clinical laboratory tests, vital signs, ECG, and immunogenicity will be summarized descriptively. Safety data will be summarized by cohort/treatment arm within each stage, as well as by avalglucosidase alfa dose levels (20 mg/kg, 40 mg/kg).
 
Analysis of pharmacokinetics and preliminary efficacy: PK parameters will be summarized for each visit and dose level using descriptive statistics. For each of the preliminary efficacy parameters, observed measurements and changes over time from pretreatment to post-baseline visit will be summarized by dose cohort/treatment arm within each stage and study visit using descriptive statistics. For those efficacy parameters that are used to identify patients who have sub-optimal response or clinical decline as part of inclusion criteria, patient profile (in terms of change over time) will be generated for those parameters where each patient will serve as his/her own control. Within Cohort 3, the effect of switching from alglucosidase alfa to avalglucosidase alfa will be assessed descriptively within each cohort/treatment arm using a composite score based on changes from pre-study to post 6 months avalglucosidase alfa treatment collected during the study. The control arm (alglucosidase alfa treatment) in Stage 2 will serve as a reference. The preliminary efficacy analysis will be performed within Cohort 3, based on

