The benefits and risks assessment of avalglucosidase alfa for the Phase 2 ACT14132 study is based upon the nonclinical studies of avalglucosidase alfa in GAA knockout mice, CD 1 mice and cynomolgus monkey studies, as well as on the results from the clinical Phase 1/2 TDR12857 study (in adult treatment-naïve late-onset Pompe disease [LOPD] patients and adult LOPD patients who had been treated with alglucosidase alfa prior to their study participation) and previous experience with alglucosidase alfa. In nonclinical studies, avalglucosidase alfa was more successful in reducing glycogen in muscle tissue compared to alglucosidase alfa. The safety profile of avalglucosidase alfa in both nonclinical and clinical studies has shown avalglucosidase alfa to be well tolerated; adverse events (AEs) and infusion-associated reactions (IARs) are mostly nonserious and usually manageable (see IB Section 7 for detailed discussion of risks). The potential benefits of avalglucosidase alfa, balanced against its known risks, support further investigation of the safety and efficacy of avalglucosidase alfa across the broad spectrum of Pompe disease, including both pediatric and adult patients.

A risk of acute cardiorespiratory failure requiring intubation and inotropic support after infusion in IOPD patients with underlying cardiac hypertrophy is considered based on experience with alglucosidase alfa and due to fluid overload. Appropriate medical support and monitoring measures should be readily available during avalglucosidase alfa infusion, and infants with cardiac dysfunction may require prolonged observation times that should be individualized based on the needs of the patient. Caution should be taken with fluid volume infusion.

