6 STUDY DESIGN

6.1 DESCRIPTION OF THE STUDY

ACT14132 is a multi-stage, phase 2, open-label, multicenter, multinational, ascending dose cohort, repeated intravenous (IV) infusion study of avalglucosidase alfa in pediatric patients with IOPD who have been previously treated with alglucosidase alfa and demonstrated clinical decline (Stage 1) or sub-optimal clinical response (Stage 2) in specified respiratory function, motor skills, cardiac parameters, and/or new onset of ptosis.

Stage 1

- Cohort 1 – at least 5 IOPD patients will receive avalglucosidase alfa at 20 mg/kg qow for 6 months.
- Cohort 2 – at least 5 IOPD patients will receive avalglucosidase alfa at 40 mg/kg qow for 6 months.

Stage 2

- Cohort 3 – at least 10 IOPD patients will be randomized 1:1 to receive avalglucosidase alfa at the highest tolerated avalglucosidase alfa dose in Stage 1 (20 mg/kg qow or 40 mg/kg qow) or alglucosidase alfa treatment at current stable dose (defined by dose of alglucosidase alfa administered regularly for a minimum of 6 months immediately prior to study entry) for 6 months. The randomization will be stratified on gender.

The first 5 patients will be enrolled in the 20 mg/kg qow dose cohort. If determined safe by an independent DMC after the 3rd patient in the 20 mg/kg qow group (Cohort 1) has received the 3rd infusion of avalglucosidase alfa and after 5 patients have started treatment in Cohort 1, the next cohort of avalglucosidase alfa at higher dose (40 mg/kg qow) will be initiated (Cohort 2). Cohort 3 will be initiated after determination of the highest tolerated avalglucosidase alfa dose in Cohort 1 and Cohort 2 after at least 5 patients in Cohort 1 and at least 5 patients in Cohort 2 have received the 7th dose of avalglucosidase alfa (or completed Week 13 with a minimum of 6 infusions).

After completion of treatment for 6 months (Week 25) and data collection for the principal analysis, the patients will continue on long-term avalglucosidase alfa treatment and follow-up in the Extension Period for up to a total of 7 years in the study. Cohort 3 patients receiving alglucosidase alfa will have the option to switch to treatment with avalglucosidase alfa in the extension period or discontinue the study. The data cut-off for the primary analysis will be after the last patient in Cohort 3 has completed 6 months of treatment (Week 25).

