1 OVERVIEW AND INVESTIGATIONAL PLAN

1.1 STUDY DESIGN AND RANDOMIZATION

ACT14132 is a multi-stage phase 2 open-label, multicenter, multinational, ascending dose cohort, repeated intravenous infusion study of avalglucosidase alfa in pediatric patients with infantile-onset Pompe disease (IOPD) who have been previously treated with alglucosidase alfa and demonstrated clinical decline (Stage 1) or sub-optimal clinical response (Stage 2) in specified respiratory function, motor skills, cardiac parameters, and/or presence of ptosis.

Stage 1:

- Cohort 1 – at least 5 IOPD patients will receive avalglucosidase alfa at 20 mg/kg every other week (qow) for 6 months.
- Cohort 2 – at least 5 IOPD patients will receive avalglucosidase alfa at 40 mg/kg qow for 6 months.

Stage 2:

- Cohort 3 – at least 10 IOPD patients will be randomized 1:1 to receive avalglucosidase alfa at the highest tolerated avalglucosidase alfa dose in Stage 1 (20 mg/kg qow or 40 mg/kg qow) or alglucosidase alfa treatment at current stable dose (defined by dose of alglucosidase alfa administered regularly for a minimum of 6 months immediately prior to study entry) for 6 months.

If determined safe by an independent Data Monitoring Committee (DMC) after the 3rd patient in the 20 mg/kg qow group (Cohort 1) has received the 3rd infusion of avalglucosidase alfa, and after 5 patients have started treatment in Cohort 1, the next cohort of avalglucosidase alfa at higher dose (40 mg/kg qow) will be initiated (Cohort 2). Cohort 3 will be initiated after determination of the highest tolerated avalglucosidase alfa dose in Cohort 1 and Cohort 2 after at least 5 patients in Cohort 1 and at least 5 patients in Cohort 2 have received the 7th dose of avalglucosidase alfa (or completed Week 13 with a minimum of 6 infusions).

Upon confirmation by the Investigator or sub-Investigator (if appropriately delegated) that the patient meets all eligibility criteria and completion of the screening and baseline assessments, in Stage 2 of the study (Cohort 3), at least 10 eligible IOPD patients will be randomized 1:1 to receive avalglucosidase alfa at the highest tolerated avalglucosidase alfa dose in Stage 1 or alglucosidase alfa treatment at current stable dose for 6 months (defined by dose of alglucosidase alfa administered regularly for a minimum of 6 months immediately prior to study entry). The randomization will be stratified on gender.

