1.3 DETERMINATION OF SAMPLE SIZE

[figure not shown]
No formal sample size calculations have been performed. Sample size for this study was based upon empirical considerations.

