2.4.4 Analyses of safety data

In general, for PAP, the summary of safety results will be presented by study cohort and treatment arm. For the overall avalglucosidase alfa treatment period, the summary of safety results will be presented by initial planned dose levels among avalglucosidase alfa patients. For Cohort 3 alglucosidase alfa patients, the summary of safety results for ETP will be presented in separate tables.

In the PAP analysis, the safety analyses will be carried out with patients by the actual treatment received, irrespective of the treatment the patient has been randomized to. The actual treatment received is defined as:

- avalglucosidase alfa if the patient receives at least one infusion with this drug in PAP;
- alglucosidase alfa if the patient only receives alglucosidase alfa in PAP.

In the ETP analysis and/or overall evaluation of avalglucosidase alfa safety, the safety analyses will be carried out by the following 3 groups:

- AVAL/AVAL in ETP includes data in ETP among patients who received avalglucosidase alfa in PAP and ETP;
- ALGLU/AVAL in ETP includes data in ETP among patients who received alglucosidase alfa in PAP and received avalglucosidase alfa in ETP;
- AVAL/AVAL and ALGLU/AVAL in overall avalglucosidase alfa treatment period includes data in PAP and/or ETP among patients who received avalglucosidase alfa in that period.

General rules

All safety analyses will be performed on the safety population as defined in [Section 2.3.1](#), unless otherwise specified, using the following common rules:

- The safety baseline value is defined the same as the baseline definition in [Section 2.1.1](#).
- The potentially clinically significant abnormality (PCSA) values are defined as abnormal values considered medically important by the Sponsor according to predefined criteria/thresholds based on literature review and defined by the Sponsor for clinical laboratory tests, vital signs, and ECG (PCSA version dated January 2014 [[Appendix B](#)]).
 - PCSA criteria will determine which patients had at least 1 PCSA during the treatment epoch (for PAP and ETP respectively), taking into account all evaluations performed during this period, including nonscheduled or repeated evaluations.
 - The number of all such patients will be the numerator for the on-treatment PCSA percentage; the denominator will be the number of patients assessed for that given parameter in the treatment epoch by treatment group on the safety population.

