- For the overall evaluation of avalglucosidase alfa safety, selected analysis will be repeated by dose levels among avalglucosidase alfa patients
- The analysis of the safety variables will be essentially descriptive and no inferential testing is planned.

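### Overall-period safety by dose level puts Stage 1 and Stage 2 patients together in one dose column and Stage 1 patients alone in the other, so dose is confounded with patient population

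*SAP*

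**What the plan says.** SAP 2.4.4 has a different rule for each period. For the 25-week primary analysis period, safety is shown by cohort and treatment arm. For the longer period: "For the overall avalglucosidase alfa treatment period, the summary of safety results will be presented by initial planned dose levels among avalglucosidase alfa patients". The section then lists three groups for the extension and overall analyses: patients on avalglucosidase alfa throughout, switchers, and the two combined. None of these identifies dose or stage. Selected analyses are to be repeated by dose level, and extension-period safety of the Cohort 3 controls goes into separate tables. "The analysis of the safety variables will be essentially descriptive and no inferential testing is planned".

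Protocol 11.4.2 also uses dose levels for the overall period. For the primary period, the protocol's clinical trial summary asks for cohort or arm within each stage, "as well as by avalglucosidase alfa dose levels (20 mg/kg, 40 mg/kg)".

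On who is in each column, SAP 1.1 says "Cohort 1 – at least 5 IOPD patients will receive avalglucosidase alfa at 20 mg/kg every other week (qow) for 6 months" and "Cohort 2 – at least 5 IOPD patients will receive avalglucosidase alfa at 40 mg/kg qow for 6 months". Protocol 6.1 describes patients who "demonstrated clinical decline (Stage 1) or sub-optimal clinical response (Stage 2)". Cohort 3 has at least 10 patients randomized 1:1. Its avalglucosidase alfa arm receives the highest tolerated Stage 1 dose, left open as 20 or 40 mg/kg. In the extension, Cohort 3 patients, including controls who switch, receive the maximum tolerated dose (Protocol 8.1.2).

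**The concern.** Because Cohort 3 gets one dose, exactly one dose column holds Stage 2 patients. A difference between the columns can then reflect who is in them as well as what they received.

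The entry criteria suggest that the two populations differ on risks the protocol itself names. Stage 1 (I 06) admits respiratory failure on invasive or non-invasive ventilation, loss of motor skills, and LVM Z-score of 6 or more or LVMI of 150 g/m² or more. Stage 2 (I 07) admits a fall in FVC or new non-invasive ventilation, a motor plateau or decrease, and new ptosis; it has no cardiac route. Protocol 4 considers "A risk of acute cardiorespiratory failure requiring intubation and inotropic support after infusion in IOPD patients with underlying cardiac hypertrophy", and Protocol 10.6 singles out cardiac hypertrophy and significantly compromised respiratory function when it asks for resuscitation equipment to be at hand.

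Safety is the primary objective of this ascending-dose study. With no tests planned, the displayed percentages are the evidence a reader will use.

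**Working it through.** **Inputs.** The minimum cohort sizes come from SAP 1.1. There is no power calculation to reproduce: "No formal sample size calculations have been performed". The only related figure is the expected total of about 20, and 5 + 5 + 10 = 20 agrees with it. The documents give no event rates by stage or dose, so every risk below is an assumption.

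**Column make-up at minimum numbers**

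| Cohort 3 dose | 20 mg/kg column | 40 mg/kg column |
|---|---|---|
| 40 mg/kg | 5, none Stage 2 | 5 + 5 = 10 (50% Stage 2); 15 (67%) if all 5 controls switch |
| 20 mg/kg | 10 (50% Stage 2); 15 (67%) if all 5 controls switch | 5, none Stage 2 |

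**Cohort 3 at 40 mg/kg.** Let p1 and p2 be the Stage 1 and Stage 2 risks without any dose effect, d the true excess at 40 mg/kg (the same in both stages), and w the Stage 2 share of the mixed column.

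- Shown at 20 mg/kg: p1
- Shown at 40 mg/kg: (1 − w)·p1 + w·p2 + d
- Shown difference: d − w·(p1 − p2)

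| p1 / p2 | True d | 20 v 40 mg/kg, n = 5 v 10 | 20 v 40 mg/kg, n = 5 v 15 |
|---|---|---|---|
| 60% / 30% | 0 | 60% v 45% | 60% v 40% |
| 60% / 30% | +15 | 60% v 60% | 60% v 55% |
| 50% / 30% | 0 | 50% v 40% | 50% v 37% |
| 50% / 30% | +15 | 50% v 55% | 50% v 52% |
| p1 = p2 | any | difference = d | difference = d |

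For example, (5 × 0.60 + 10 × 0.30)/15 = 0.40, and (5 × 0.75 + 10 × 0.45)/15 = 0.55.

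**Cohort 3 at 20 mg/kg.** The shown difference becomes d + w·(p1 − p2). With 60% / 30% and no dose effect, the table reads 45% v 60% (10 v 5 patients) or 40% v 60% (15 v 5). That is a spurious excess of 15 or 20 points at 40 mg/kg.

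**How low must the Stage 2 risk be?** Take decliners at 40% on 20 mg/kg and 60% on 40 mg/kg, a true +20 points, and let s be the Stage 2 risk on 40 mg/kg. The shown difference, in points, is (1 − w)·60 + w·s − 40.

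| s | n = 5 v 10 | n = 5 v 15 |
|---|---|---|
| 60% | +20 | +20 |
| 40% | +10 | +6.7 |
| 30% | +5 | 0 |
| 20% | 0 | −6.7 |
| 10% | −5 | −13.3 |

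**Sampling noise.** Under the same true +20 points, exact binomial calculation gives the chance that the observed percentage at 40 mg/kg is no higher than at 20 mg/kg:

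- Cohort 1 v Cohort 2 (5 v 5): 37%
- Pooled with 5 Stage 2 patients at 20% risk: 57%
- Pooled with 10 Stage 2 patients at 20% risk: 65%

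**The case against.** The strongest reply is that the decisions that matter do not use these displays. That stands in full. The data monitoring committee reviews Cohorts 1 and 2 before Cohort 3 starts, and the maximum tolerated dose is set from those two cohorts (Protocol 6.4.1 and 8.1.2). The primary adverse-event analysis covers the first 25 weeks, where the SAP tabulates by cohort and arm. The protocol's primary-period dose-level summary sits beside tables within stage.

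Next, the SAP names cohort in other places. The general paragraph of 2.4.4.1 says adverse-event summaries are by cohort and treatment group, and selected primary-period analyses are to be repeated for the overall period. Laboratory summaries by visit (2.4.4.3), vital-sign abnormalities (2.4.4.4), physical examination (2.4.4.6) and immunogenicity (2.4.4.7) also mention cohort. This stands in part. Those summaries are less exposed, but a general line and an unspecified selection neither override the specific overall-period rule nor guarantee an overall adverse-event table within stage. The potentially clinically significant laboratory and ECG abnormalities are specified by treatment group without naming cohort.

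Third, that Stage 2 patients carry lower risk is an inference. All patients need cardiomyopathy at diagnosis (I 04), the Stage 1 motor criterion up to age 2 (failure to gain milestones) is close to the Stage 2 plateau, and Stage 2 admits an FVC decline of 15% or more. This stands, so the direction and size of the bias are conditional. The 15-patient column also assumes that every control switches, and they may instead leave the study.

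Last, with 5 patients per cohort no split will reliably reveal harm; the 37% above shows that. This is true, but it is no reason to add avoidable confounding.

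A reader might infer that the plan will make 40 mg/kg look safer and that the Cohort 1 v Cohort 2 contrast is lost. The documents do not support this. The Cohort 3 dose is left open, so the bias could run either way, and the unmixed contrast is available for the primary period.

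**Conclusion.** The point holds in a limited form. In the overall-period dose-level displays, dose is confounded with stage whichever of the two planned doses Cohort 3 receives. The exposed summaries are chiefly adverse events, serious adverse events, infusion-associated reactions and potentially clinically significant abnormalities. On the assumed 60% and 30% risks with 5 v 15 patients, the distortion is 20 points: enough to turn a true 15-point excess at 40 mg/kg into an apparent 5-point advantage. It reverses if Cohort 3 is at 20 mg/kg and is zero if the stages carry equal risk. These figures rest on assumed rates, minimum cohort sizes, all controls switching, and switchers being counted at the same dose level as the rest of Cohort 3. The by-cohort primary-period tables and the determination of the maximum tolerated dose are untouched. The change is worth making because it is cheap and these displays describe long-term safety, but it does not undermine the primary analysis.

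**What to change.** In SAP 2.4.4, and in Protocol 11.4.2 for the overall period, present the adverse-event, serious adverse-event, infusion-associated-reaction and abnormality summaries in separate columns: Cohort 1, Cohort 2, Cohort 3 avalglucosidase alfa, Cohort 3 switchers, and a total. State that any descriptive dose comparison is read from Cohort 1 v Cohort 2. If pooled dose-level columns are kept, label them as mixing stages.

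The cost is SAP wording and extra table columns; no new data are needed. The downside is about 5 patients per column, so percentages should be read with their counts. One limit remains: Cohort 1 patients may move to 40 mg/kg in the extension and would stay under their initial planned dose, so the overall-period Cohort 1 column can include time at the higher dose. The dose-change listing in SAP 2.2 should be cited beside it.
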